8.2.2 Special Assays or Procedures

Oxfendazole drug concentrations will be performed by [name] lab at the University of Iowa.

Blood samples for PK analysis will be collected in tubes containing sodium heparin as the anticoagulant at baseline. The blood samples (10 mL) will be placed on ice after draw, and centrifuged within 1 hour at 4-8°C at approximately 3000 rpm for 15 min. The plasma will then be collected and stored frozen at -80°C until analyzed. Plasma samples will be shipped to the analytical lab frozen. Validated methods will be used to assay the oxfendazole concentration in each sample.

8.2.3 Specimen Preparation, Handling, Storage, and Shipping

8.2.3.1 Instructions for Specimen Preparation, Handling, Storage, and Shipping

Instructions for specimen preparation, handling, storage, and shipping are included in the MOP.

9 ASSESSMENT OF SAFETY

9.1 Specification of Safety Parameters

Safety outcome measures are defined in Section 3.2 and include the rate of SAEs and non-serious severe AEs.

9.2 Methods and Timing for Assessing, Recording, and Analyzing Safety Parameters

9.2.1 Adverse Events

Adverse Event:

ICH E6 defines an AE as any untoward medical occurrence in a patient or clinical investigation subject administered a pharmaceutical product regardless of its causal relationship to the study treatment. An AE can therefore be any unfavorable and unintended sign (including an abnormal laboratory finding), symptom, or disease temporally associated with the use of medicinal (investigational) product. The occurrence of an AE may come to the attention of study personnel during study visits and interviews of a study recipient presenting for medical care, or upon review by a study monitor.

All AEs including local and systemic reactions not meeting the criteria for “serious adverse events” should be captured on the appropriate CRF. Information to be collected includes event description, time of onset, clinician’s assessment of severity, relationship to study product (assessed only by those with the training and authority to make a diagnosis, which would include MD, PA, Nurse Practitioner, DO, or DDS), and time of resolution/stabilization of the event. All AEs occurring while on study must be documented appropriately regardless of relationship. All AEs will be followed to adequate resolution.

Any medical condition that is present at the time that the patient is screened should be considered as baseline and not reported as an AE. However, if it deteriorates at any time during the study, it should be recorded as an AE.

All AEs must be graded for severity and relationship to study product.

FDA defines an AE as any untoward medical occurrence associated with the use of a drug in humans, whether or not considered drug related.

Severity of Event: All AEs will be assessed by the clinician using a protocol defined grading system. For events not included in the protocol defined grading system, than the following guidelines will be used to quantify intensity.

Grade 1: Mild: events require minimal or no treatment and do not interfere with the patient's daily activities.

Grade 2: Moderate: events result in a low level of inconvenience or concern with the therapeutic measures. Moderate events may cause some interference with functioning.

Grade 3: Severe: events interrupt a patient's usual daily activity and may require systemic drug therapy or other treatment. Severe events are usually incapacitating.

Changes in the severity of an AE should be documented to allow an assessment of the duration of the event at each level of intensity to be performed. Adverse events characterized as intermittent require documentation of onset and duration of each episode.

Relationship to Study Products: The clinician's assessment of an AE's relationship to test article (vaccine or study drug) is part of the documentation process, but it is not a factor in determining what is or is not reported in the study. If there is any doubt as to whether a clinical observation is an AE, the event should be reported. All AEs must have their relationship to study product assessed using the terms: related or not related. In a clinical trial, the study product must always be suspect. To help assess, the following guidelines are used.

- Related – There is a reasonable possibility that the study product caused the adverse event. Reasonable possibility means that there is evidence to suggest a causal relationship between the study product and the adverse event.
- Not Related – There is not a reasonable possibility that the administration of the study product caused the event.

9.2.2 Serious Adverse Events

Serious Adverse Event (SAE):

An adverse event or suspected adverse reaction is considered "serious" if, in the view of either the investigator or sponsor, it results in any of the following outcomes:

- Death,
- a life-threatening adverse event*,
- inpatient hospitalization or prolongation of existing hospitalization,
- a persistent or significant incapacity or substantial disruption of the ability to conduct normal life functions, or

-
- a congenital anomaly/birth defect.
 - Important medical events that may not result in death, be life-threatening, or require hospitalizations may be considered serious when, based upon appropriate medical judgment they may jeopardize the patient or subject and may require medical or surgical intervention to prevent one of the outcomes listed in this definition. Examples of such medical events include allergic bronchospasm requiring intensive treatment in an emergency room or at home, blood dyscrasias or convulsions that do not result in inpatient hospitalization, or the development of drug dependency or drug abuse.

* Life-threatening adverse event. An adverse event is considered “life-threatening” if, in the view of either the investigator or sponsor, its occurrence places the patient or subject at immediate risk of death. It does not include an adverse event, had it occurred in a more severe form, might have caused death.

All SAEs will be:

- recorded on the appropriate SAE CRF
- followed through resolution by a study clinician
- reviewed and evaluated by a study clinician

9.2.3 Procedures to be Followed in the Event of Abnormal Laboratory Test Values or Abnormal Clinical Findings

The site principal investigator or appropriate sub-investigator is responsible for reporting all AE/SAEs that are observed or reported during the study, regardless of the relationship to study product. All clinically significant EKG abnormalities will be reported as an AE.

AE/SAEs, abnormal clinical laboratory test values or clinically significant EKG changes, or abnormal clinical findings will be documented, reported, and followed until the event has resolved or has stabilized.

If baseline clinical labs fall within Grade 1 parameters, then an AE is reported only if the value changes such that it falls into Grade 2 or higher at subsequent visits. For laboratory results that are abnormal according to the local laboratory reference range, but not considered a Grade 1 abnormality, these will not be considered AEs and will thus not be graded, but will be followed-up clinically at the discretion of the study site physician.

9.3 Reporting Procedures

AEs will be documented from the time of receipt of study drug on Day 1 (Visit 02) through the final study visit (approximately 10 or 14 days after receipt of study product).

SAEs will be documented from the time of receipt of study drug on Day 1 (Visit 02) through the final study visit.

AEs will be followed until resolution even if this extends beyond the study-reporting period. Resolution of an AE is defined as the return to pretreatment status or stabilization of the condition with the expectation that it will remain chronic.

9.3.1 Serious Adverse Events

Any AE that meets a protocol-defined serious criterion must be submitted immediately (within 24 hours of site awareness) on an SAE form to the DMID Pharmacovigilance Group, at the following address:

**DMID Pharmacovigilance Group
Clinical Research Operations and Management Support (CROMS)
[name] [name] 650
Bethesda, MD 20817, USA
SAE Hot Line: [name] (US) or [name] (outside US)
SAE FAX [contact] (US) or [name] (outside US)
SAE Email Address: [contact]**

Other supporting documentation of the event may be requested by the DMID Pharmacovigilance Group and should be provided as soon as possible.

The DMID medical monitor and clinical protocol manager will be notified of the SAE by the DMID Pharmacovigilance Group. The DMID medical monitor will review and assess the SAE for regulatory reporting and potential impact on study subject safety and protocol conduct.

At any time after completion of the study, if the investigator becomes aware of an SAE that is suspected to be related to study product, the investigator will report the event to the DMID Pharmacovigilance Group.

9.3.2 Regulatory Reporting for Studies Conducted Under DMID-Sponsored IND

Following notification from the investigator, DMID, the IND sponsor, will report any suspected adverse reaction that is both serious and unexpected. DMID will report an adverse event as a suspected adverse reaction only if there is evidence to suggest a causal relationship between the drug and the adverse event. DMID will notify FDA and all participating investigators (i.e., all investigators to whom the sponsor is providing drug under its INDs or under any investigator's IND) in an IND safety report of potential serious risks from clinical trials or any other source, as soon as possible, but in no case later than 15 calendar days after the sponsor determines that the information qualifies for reporting as specified in 21 CFR Part 312.32. DMID will also notify FDA of any unexpected fatal or life-threatening suspected adverse reaction as soon as possible but in no case later than 7 calendar days after the sponsor's initial receipt of the information. Relevant follow up information to an IND safety report will be submitted as soon as the information is available. Upon request from FDA, DMID will submit to FDA any additional data

or information that the agency deems necessary, as soon as possible, but in no case later than 15 calendar days after receiving the request.

All serious events designated as “not related” to study product(s), will be reported to the FDA at least annually in a summary format.

9.3.3 Regulatory Reporting for Studies Not Conducted Under DMID-Sponsored IND

N/A.

9.3.4 Other Adverse Events (if applicable)

N/A

9.3.5 Reporting of Pregnancy

Pregnancies occurring in study subjects will be reported in IDES. No further study medication will be administered to pregnant subjects, but all study-mandated blood samples will be obtained and the subject will continue in follow-up for safety events. Pregnancies will be followed to pregnancy outcome pending the subject’s permission.

9.4 Type and Duration of Follow-up of Subjects after Adverse Events

AEs and SAEs will be followed from the time of the first receipt of study drug Day 1 (Visit 02) through the last subject’s study visit.

AEs and SAEs will be followed until resolution even if this extends beyond the study-reporting period. Resolution of an AE/SAE is defined as the return to pretreatment status or stabilization of the condition with the expectation that it will remain chronic.

If the site principal investigator or appropriate sub-investigator becomes aware of a sign or symptom and the site principal investigator or appropriate sub-investigator decides to bring the subject in for an evaluation to determine etiology, then the site principal investigator or appropriate sub-investigator, at their own discretion, can determine what further testing is appropriate.

Follow-up procedures, evaluations, and outcomes will be recorded on the appropriate data collection form.

9.5 Halting Rules

9.5.1 Sentinel Subject Halting Rules

For each of the multiple dose ascending groups (Groups 1-3), one sentinel subject will be dosed and monitored for 7 days after receiving the first dose of study product. If there are no

predefined safety events, a second sentinel subject will be enrolled and followed for a total of 7 days. If none of the sentinel subjects' halting criteria are met:

- any study drug related SAE
- any study drug related grade 3 AE or laboratory abnormality
- any two Grade 2 AE or laboratory abnormalities of the same laboratory parameter that are study drug related

then the remaining subjects in each group may be enrolled.

9.5.2 Dose Escalation Halting Criteria

Prior to dose escalation to the next cohort, the Statistical and Data Coordinating Center (SDCC) will notify the study PIs, DMID medical monitor (MM), and DMID Independent Safety Monitor (ISM) whether the below dose escalation criterion were met. Following enrollment and 10 days of safety follow up of the eight subjects in the dose group.

Dose escalation will not proceed if any of the following dose escalation criteria occur:

- any study drug related SAE
- any study drug related grade 3 AE or laboratory abnormality
- any two Grade 2 AE or laboratory abnormalities of the same laboratory parameter

In addition to these criteria, dose escalation may also stop for other reasons per the advice of the SMC, ISM, or DMID Medical Monitor for further evaluation, discussion, and recommendations from the SMC.

If the above dose escalation halting criteria are NOT met, the dose escalation may proceed with agreement of DMID.

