Description of Study Design:	This Phase I study is an open label evaluation of the safety and pharmacokinetics of escalating oral doses of oxfendazole (3 mg/kg, 7.5 mg/kg or 15 mg/kg) given daily for five days in healthy volunteers. Up to eight volunteers will be enrolled and receive one oral dose of 3 mg/kg given daily for 5 days. To enhance safety, one sentinel subject will be enrolled and followed for 7 days for defined safety events. A second sentinel subject will then be enrolled and followed for 7 days. If no

[figure not shown]
predefined safety events are identified, the remaining six subjects in this group will be enrolled. All volunteers will be followed for 10 days and pharmacokinetic, safety laboratory and EKG studies will be performed as outlined in the study visit table in Appendix A. A safety review of the electronic data will be completed and the DMID Medical Monitor will receive a dose escalation report from the Statistical and Data Coordinating Center (SDCC) including whether dose escalation halt criteria were or were not met. If no predefined safety events occur after all eight subjects have completed the day 10 visit, the DMID Medical Monitor will issue approval to proceed with enrollment of the second group of eight subjects will be enrolled to receive five days of 7.5 mg/kg of oxfendazole using the same enrollment plan as outlined above. If no predefined safety events are encountered, the third group of eight subjects will be enrolled to receive five days of 15 mg/kg using the same enrollment plan. A fourth group of 12 subjects will participate in a single dose cross over evaluation of the effects of food on the pharmacokinetics of oxfendazole. Half of these subjects will fast for 8 hours and then will receive a single dose of 3 mg/kg of oxfendazole on day 1. The other half will receive a single dose of 3 mg/kg of oxfendazole following a high fat breakfast. All 12 subjects will be followed for seven days and on day 8 each subject will cross over to receive drug following a high fat breakfast or following an 8 hour fast and will be followed for another seven days. Pharmacokinetic studies will be performed for 24 hours following each dose of oxfendazole.

Group	N	Study Dose	Timing of Study Dosing
1	8	3 mg/kg	Days 1-5
2	8	7.5 mg/kg	Days 1-5
3	8	15 mg/kg	Days 1-5

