4 STUDY DESIGN

This Phase I study is an open label multiple ascending dose evaluation of the safety and PK of oxfendazole (3, 7.5, or 15 mg/kg) in healthy adult men and nonpregnant women aged 18-45 (inclusive) followed by a single dose cross over trial evaluating the safety and pharmacokinetics of a single dose of oxfendazole (3 mg/kg) given following an 8 hour fast or following a high fat meal. In the multiple ascending dose evaluation, each dose group will be comprised of eight volunteers. In the food effects evaluation, evaluating the effects of food on drug absorption, 12 subjects will be enrolled into the single dose cross over group where half of the subjects will initially receive a single dose of 3 mg/kg of oxfendazole following an 8 hour fast and the other half will receive a single dose of 3 mg/kg of oxfendazole following a high fat meal. Subjects will then cross over to receive a single dose following a high fat breakfast or fasting period (water is permitted). All subjects will have received a single dose of oxfendazole (3 mg/kg) following both a fasting period and a meal.

For the multiple ascending dose evaluation, each subject in the first dose group (3 mg/kg) will receive an oral daily dose of oxfendazole for five sequential days and will be monitored for a total of 10 days. Each subject will be followed with blood, urine and EKG studies for safety and will provide plasma samples for oxfendazole PK studies as outlined in the study visit schedule in Appendix A. To enhance safety, one sentinel subject will be dosed for five days and monitored for 7 days from the time of the first dose for predefined adverse events, which will include any drug related SAEs, any study drug-related Grade 3 AEs or laboratory abnormalities or two study drug-related Grade 2 AEs or laboratory abnormalities in the same laboratory parameter. If there are no predefined safety events, a second sentinel subject will be enrolled and followed for a total of 7 days. If there are no predefined safety signals identified for either of these two sentinel subjects, the remaining subjects in the group will be enrolled.

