After all eight subjects have completed the 10 day follow up period, an electronic safety review of the electronic data will be performed and the SDCC will issue a report to DMID stating that the predefined halting rules have or have not been met. If none of the predefined safety events (any study drug related SAE, any study drug related Grade 3 AE or laboratory abnormality or two study drug related Grade 2 AEs or laboratory abnormalities in the same laboratory parameter) have occurred (one study drug related two sequential subjects (one at a time with 7 days between each subject) DMID will approve enrollment into the second dose group (7.5 mg/kg oxfendazole daily x 5 days) and will be monitored for a total of 7 days each for predefined adverse events prior to enrolling the remaining subjects in the group. After the 10 day follow up period has been completed for group 2, an electronic safety review will be completed and if no predefined events have occurred two sequential subjects (one at a time with 7 days between each subject) will be enrolled into the third dose group (15 mg/kg oxfendazole daily x 5 days) and will be monitored for a total of 7 days each for predefined safety events prior to enrolling the remaining subjects in the group.

For the multiple ascending dose evaluation, between 8 and 24 subjects will be enrolled. This number should be small enough to perform the study safely and efficiently, yet large enough for an estimation of the oxfendazole PK and the identification of any common side effects of oxfendazole following multiple doses.

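### Sections 4 and 9.5.2 of the protocol give different Grade 2 rules for the same dose-escalation decision: one requires relatedness to study drug, the other does not.

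*Protocol*

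**What the plan says.** The decision to move from 3 to 7.5 mg/kg, and then to 15 mg/kg, is described in two places in the protocol.

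- **Section 4 (Study Design).** After all eight subjects finish the 10-day follow-up, the statistical and data coordinating center (SDCC) reports whether the halting rules were met. The blocking events are listed as any related SAE, any related Grade 3 event, or "two study drug related Grade 2 AEs or laboratory abnormalities in the same laboratory parameter". If none has occurred, "DMID will approve enrollment into the second dose group".
- **Section 9.5.2 (Dose Escalation Halting Criteria).** After the same eight subjects and 10 days, the SDCC again notifies whether criteria were met. "Dose escalation will not proceed if any of the following dose escalation criteria occur". The SAE and Grade 3 bullets are limited to study-drug-related events. The Grade 2 bullet reads only "any two Grade 2 AE or laboratory abnormalities of the same laboratory parameter".

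The sentinel rule, a separate and earlier gate, carries the relatedness condition for Grade 2 in both of its statements: "two study drug-related Grade 2 AEs or laboratory abnormalities in the same laboratory parameter" in Section 4 and "any two Grade 2 AE or laboratory abnormalities of the same laboratory parameter that are study drug related" in Section 9.5.1.

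The Protocol Summary says "If no predefined safety events occur after all eight subjects have completed the day 10 visit, the DMID Medical Monitor will issue approval", and SAP Section 2.1 says much the same. Neither defines the events; Section 4 does, with the relatedness condition. The Summary also says that the SDCC report covers the dose escalation halt criteria, which points towards 9.5.2.

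**The concern.** A halting criterion has to give one answer for any set of data. Here the SDCC must issue a binary statement, and the two texts that define it differ on whether causality matters for Grade 2 events. The difference bites because every adverse event is classed as related or not related (Section 9.2.1), so an unrelated Grade 2 event is a routine recorded outcome.

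What turns on it is whether escalation pauses. Under Section 9.6, the only scheduled SMC meeting before the final review comes after Group 3 has completed day 10, so neither escalation step has a planned SMC review. Section 9.6.2 names a dose escalation rule being met as an occasion for ad hoc review, so the wording decides whether that occasion arises. The human data cited in support of these five-day regimens come from a single-dose study.

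**Working it through.** **Step 1. Do the texts cover the same decision?** Yes. Both concern eight subjects, 10 days of follow-up, an SDCC met/not-met report, and enrollment of the next dose group.

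**Step 2. Apply both rules to the same data.** Take two Grade 2 abnormalities in one laboratory parameter within a cohort, and nothing else of note.

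| Causality of the two events | Section 9.5.2 | Section 4 |
|---|---|---|
| Both related | met | met |
| One related, one not | met | not met |
| Neither related | met | not met |

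The rules disagree in two of the three rows. In both rows 9.5.2 blocks escalation and Section 4 allows it.

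**Step 3. Can the missing condition be read in?** Not from the text. Within the 9.5.2 list the other two bullets state relatedness and the third does not. The sentinel bullet in 9.5.1 has the same words as the 9.5.2 Grade 2 bullet and then adds the condition. Three of the four statements of a Grade 2 rule carry it and one does not. Read literally, 9.5.2 ignores an unrelated Grade 3 laboratory abnormality but stops for two unrelated Grade 2 abnormalities in the same parameter. That suggests a drafting omission, but a deliberately stricter rule cannot be excluded.

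**Step 4. Is the situation plausible?** Section 2.3.1 reports 7 moderate hematology and 6 moderate biochemistry results in the earlier study: 7 + 6 = 13 among 70 subjects, with similar rates of abnormal tests on placebo. Unrelated Grade 2 values are therefore plausible. The 13 are not split by parameter or by subject, so they cannot be turned into a rate.

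**Step 5. Illustrations under assumed rates.** The chance that at least 2 of 8 independent subjects have an event of per-subject probability p is T(p) = 1 − (1−p)^8 − 8p(1−p)^7.

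*Laboratory values.* Let p be the assumed chance of an unrelated Grade 2 value in one given parameter, in a cohort with no related event:

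- p = 0.01: T = 0.003
- p = 0.02: T = 0.010
- p = 0.05: T = 0.057
- p = 0.10: T = 0.187

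These are for one parameter. With 15 blood safety parameters treated as independent (a rough assumption), the chance in at least one parameter is 1 − (1−T)^15: about 0.04, 0.14 and 0.59 at p = 0.01, 0.02 and 0.05.

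*Clinical adverse events.* Section 2.1.2 reports one moderate related event. Take the related rate r as 1/70 (all subjects) or 1/56 (7 groups × 8 dosed), let f be the share of events judged related, and set the any-cause rate to r/f. The chance of disagreement is T(r/f) − T(r).

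| f | r = 1/70 | r = 1/56 |
|---|---|---|
| 0.75 | 0.0094 − 0.0054 = 0.004 | 0.0144 − 0.0083 = 0.006 |
| 0.50 | 0.0204 − 0.0054 = 0.015 | 0.0309 − 0.0083 = 0.023 |
| 0.25 | 0.0726 − 0.0054 = 0.067 | 0.1071 − 0.0083 = 0.099 |

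This assumes at most one event counted per subject, that any two clinical events qualify, that moderate means Grade 2, and that a single-dose rate carries over to five doses.

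**The case against.** The best case against acting is that 9.5.2 is plainly the operative text. It is the dedicated section, its title matches the term the Summary uses for the SDCC report, and Section 4 itself refers the SDCC to the halting rules, which are in Section 9.5. A programmer would normally build the report from that list. It is also the stricter version, so following it costs at most an unneeded pause. The Section 4 sentence is visibly garbled and so is weak evidence of mandatory approval. Under 9.5.2 escalation needs DMID's agreement in any case, "dose escalation may also stop for other reasons per the advice of the SMC, ISM, or DMID Medical Monitor", and Section 9.5.3 lets DMID suspend enrollment and dosing at any time.

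Most of this stands as a limit on the practical risk. It does not remove the conflict. Section 4 restates the blocking events itself, with the condition attached, and the Summary ties approval to the absence of those predefined events in a sentence that is not garbled there. Discretion to stop is not the same as a rule that stops.

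The objection to the percentages is also fair. The clinical illustration rests on one event, and the related share is a choice. The earlier study classed 6 of 16 unsolicited events as related; at f = 6/16 = 0.375 the same formula gives 3.0% to 4.4%. The 1/70 rate also counts 14 placebo subjects. The conclusion does not use these figures.

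**Conclusion.** The inconsistency is real and lies in current protocol text. For a pair of Grade 2 abnormalities in one laboratory parameter, at least one judged unrelated, the protocol gives opposite instructions on escalating the dose in healthy volunteers, and nothing in it sets precedence. This follows from the wording alone.

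The frequency of disagreement is unknown. Under the stated assumptions the clinical-event illustration spans 0.4% to 9.9% of cohorts, and the laboratory figures depend entirely on the assumed p. The harm is bounded because related events stop escalation under either text, and the safety estimates and PK analyses do not depend on the choice. It should be corrected before the first escalation decision, but it does not undermine the design.

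**What to change.** Before the first escalation decision, use one Grade 2 wording in both sections and program the SDCC report to it.

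- **Simplest option:** add the relatedness condition to the third bullet of 9.5.2, so that it matches Section 4 and the sentinel rule.
- **If an any-cause rule is intended:** remove the condition from the Grade 2 escalation item in Section 4. The sentinel and escalation rules would then differ, so the term for predefined safety events, which the Summary and SAP Section 2.1 use for both gates, should be defined separately for each.

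Under either option, repair the garbled escalation sentence in Section 4 at the same time. Until the text is amended, apply the stricter 9.5.2 wording.

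The cost is a short amendment or clarification letter and a check of the SDCC report. Relatedness is already recorded for every adverse event, so no new data are needed. Keeping the any-cause rule would add an occasional pause for SMC review.
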